Additionally, B-PEth-level analysis compared to baseline levels will also be performed for Day7, Day 21, Day 35, Day 49, Day 63 and Day 77. B-PEth has a well-documented declining pattern and hence it follows that the mean value during the treatment period will be a sufficient statistic for the post-treatment level. B-PEth will be collected initially at the screening visit and onwards from randomization visit every 2nd week during the study (except for the first visit, which is one week after randomization). An analysis with regards to B-PEth, will be performed using an analysis of covariance (ANCOVA) using the mean value of B-PEth (day21-day77) within patient, as the dependent variable. Adjustments for following covariates will be performed: treatment group, center, nicotine use (Yes/No) and family history positive, FHP (Yes/No).

The ANCOVA model will have fixed effects for treatment and center and subject, nicotine use and FHP will be entered as random effect.

Baseline B-PEth will be used as a covariate in the analysis.

- **Heavy Drinking Days (HDD)**

The additional main outcome will be alcohol consumption as measured by Heavy Drinking Days (HDD) using the Time Line Follow Back (TLFB) procedure. The number of heavy drinking days HDD by 14 days is defined as a mean over the 8-week steady state active treatment period (Day 21 -Day 77) compared to baseline. A HDD is defined in two ways; as ≥ 60 grams for men and ≥ 40 for women according to EMA's guideline and as ≥ 70 grams for men and ≥ 56 grams for women according to FDA's guideline on the development of medicinal products for the treatment of alcohol dependence. The baseline mean of heavy drinking days by 14 days, is obtained at the screening visit, where the number of heavy drinking days over the last 30 days is registered.

The number of heavy drinking days, "HDD 21-77", is the total number of heavy drinking days divided by 4 (8weeks/2), in order to get a 14 day-period measurement. The maximum total number of days measured is 56 days. Additionally, HDD analysis compared to baseline levels will also be performed for Day7, Day 21, Day 35, Day 49, Day 63 and Day 77 and parts of the 8 week steady state active treatment period.

Adjustment for the covariates treatment group, smoking (Yes/No), family history positive, FHP, (Yes/No) and center will be performed. Baseline alcohol consumption will be used as a covariate in the analysis. The

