ANCOVA model will have fixed effects for treatment and center and subject, nicotine use and FHP will be entered as random effect.

Definition of analysis sets

Three analysis sets will be used: Modified Intention-To-Treat (mITT), Per Protocol (PP) and Safety. The primary and secondary efficacy endpoints will be estimated using ITT and PP analysis sets separately. The safety endpoints will be analyzed on the safety analysis set.

1) Modified Intention-to-treat (mITT) analysis set

The mITT analysis set will include all trial subjects who complete screening visit and randomization visit and report that they have taken at least one dose of the randomized IMPs. Subjects will be analyzed according to their randomized IMPs.

2) Per-protocol (PP) analysis set

The PP analysis set constitutes all subjects from the ITT population who are considered to be completers. A completer is defined as a subject who:

- has taken the IMP at least 80% of the planned number of days of the active treatment period
- fulfill the visit milestones, where the visit milestones are met by subjects who have:
 - taken part and completed screening visit, Day 0, Day 21, Day 49 and Day 77
 - successful B-PEth analyses at screening visit, Day 0, Day, 21, Day 49 and Day 77
 - completed TLFB data at screening visit, Day 0, Day, 21, Day 49 and Day 77

In case of violation of any of the above-mentioned criteria the subject will not be included in the PP analysis set for the specific outcome variable. Subjects will be analyzed according to their randomized study drug.

3) Safety set

The safety analysis set includes all subjects who report that they have taken at least one dose of randomized study drug, and for whom any post-dose data is available up until Day 77. Patients will be analyzed according to the actual treatment.

Compliance

Adherence to the study drug regimen will be analyzed by pill count and by plasma levels of IMP1 and IMP2 at visit 4 and visit 6.

Randomization issues

Mistakenly randomizing a subject who does not meet the inclusion/exclusion criteria will be considered a protocol violation. Any such subject will not be included in the analysis sets.

Handling of missing data

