Handling of missing data in the alcohol consumption data as measured by TLFB. In a blind data review, missing data will be assessed. If found appropriate, since we expect that the missing data are not at random, due to the tendency of alcohol patients to have a drinking pattern, we will handle the missing data not by last observation carried forward (LOCF), but instead by an imputation taking the subjects pattern into account. The missing day will be imputed by the data from the same weekday in the weeks before and after, if possible. To adjust for changes in alcohol consumption over time, the weeks closest to the missing day will have a greater weight than the weeks more distant from the missing day.

If a subject drops out from the study in early treatment, the baseline observation will be carried forward. If the subject drops out late in the treatment period the last observed 7 days will be carried forward, if there are missing days, these will be imputed as described above. This model allows for the probability that a longer treatment period will have a greater impact on the alcohol consumption. For all other variables missing data will be considered missing and no imputation will be computed.

All statistical concerns and estimations are described in a separate statistical protocol, the Statistical Analysis Plan (SAP).

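### The primary heavy-drinking score divides by a fixed 4, so any day in the window left without a measured or imputed value is scored as non-heavy

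*Protocol*

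**What the plan says.** Protocol section 8.2, under Heavy Drinking Days, says that the outcome "is defined as a mean over the 8-week steady state active treatment period (Day 21 -Day 77) compared to baseline". The score itself "is the total number of heavy drinking days divided by 4 (8weeks/2), in order to get a 14 day-period measurement". The next sentence adds: "The maximum total number of days measured is 56 days". No minimum is given, and the divisor is not tied to the number of days available.

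The comparator is on a 14-day scale too: "The baseline mean of heavy drinking days by 14 days, is obtained at the screening visit", from a 30-day calendar. The section also plans HDD analyses for parts of the 8 weeks.

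Under Handling of missing data, section 8.2 describes imputation for the drinking calendar. Its opening condition, to be settled at a blind data review, is "If found appropriate, since we expect that the missing data are not at random". For single days: "The missing day will be imputed by the data from the same weekday in the weeks before and after, if possible", with nearer weeks weighted more heavily. For dropout: "If a subject drops out from the study in early treatment, the baseline observation will be carried forward", while a late dropout has the final week of observed data carried forward. Nothing is said about a day that still has no value after these steps, or about whether the HDD total is taken before or after them.

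**The concern.** A total over fewer than 56 valued days, divided by 4, is no longer a rate per 14 days. The missing days add nothing to the numerator but stay in the denominator, so they count as non-heavy. Whichever arm has more such days looks better on a primary endpoint for that reason alone. The protocol itself expects drinking data to be missing not at random, so a non-heavy default is hard to defend as neutral.

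The formula also sits awkwardly with the text around it:

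- Section 8.1 states the HDD hypothesis and its detectable effect as a proportion of days. Total/4 equals 14 times that proportion only with 56 valued days.
- A 30-day baseline count expressed per 14 days has to be rescaled by the days covered (14/30). The on-treatment score has no such rescaling.
- A divisor of 4 cannot serve the planned sub-period analyses. A 28-day part, for example, would need 28/14 = 2.

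**Working it through.** **Inputs from the protocol.** Window 56 days, divisor 4 (section 8.2). HDD detectable difference 15%, that is 0.15, with SD 0.35 (section 8.1).

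**Assumed.** The share p of days that are heavy is not given; I use 0.3, 0.5 and 0.7. Leftover days are taken to have the same p as the subject's other days. For the between-arm step, p is taken as equal in the two arms.

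**1. The plan's own figures.** 56/14 = 4, so the divisor reproduces for a full window. The standardized effect also reproduces: 0.15/0.35 = 0.43.

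**2. Score with m valued days.** Let m be the number of days with a measured or imputed value.

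- Fixed divisor: p × m / 4
- Days-based: 14 × (p × m) / m = 14p
- Shortfall: 14p − pm/4 = p × (56 − m) / 4

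| Valued days m | p | Fixed divisor | Days-based | Shortfall |
|---|---|---|---|---|
| 56 | 0.5 | 7.00 | 7.00 | 0 |
| 55 | 0.3 | 4.125 | 4.20 | 0.075 |
| 55 | 0.5 | 6.875 | 7.00 | 0.125 |
| 55 | 0.7 | 9.625 | 9.80 | 0.175 |
| 42 | 0.3 | 3.15 | 4.20 | 1.05 |
| 42 | 0.5 | 5.25 | 7.00 | 1.75 |
| 42 | 0.7 | 7.35 | 9.80 | 2.45 |

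Each leftover day therefore costs p/4, which is 0.075 to 0.175 heavy days per 14.

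**3. Between-arm effect.** On the proportion scale the shortfall is p × u, where u = (56 − m)/56 is the share of days left without a value. If u differs by 0.10 between two arms, the comparison shifts by 0.10 × p:

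- p = 0.3: 0.03, and 0.03/0.15 = 20% of the detectable difference
- p = 0.5: 0.05, and 0.05/0.15 = 33%
- p = 0.7: 0.07, and 0.07/0.15 = 47%

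**4. Equal shares in both arms.** With u = 0.10 in each arm, a true difference of 0.15 becomes 0.15 × (1 − 0.10) = 0.135. That is mild attenuation, not a shift in favour of one arm.

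**5. Full imputation.** Then m = 56, u = 0 and the bias is zero.

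**The case against.** The strongest reply is that section 8.2 already fills the calendar. The two dropout rules are stated without the opening condition, and dropout may well be the largest source of missing days. Once the days are filled, 4 is exactly right. This stands, and it limits the point: a reader might infer that every unmeasured day counts as non-heavy, and the protocol does not support that. What remains is the intermittent day for which imputation is judged inappropriate or has no usable neighbouring week.

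A reader might also infer that a per-protocol completer could have only 28 of the 56 days. The milestone list requires "completed TLFB data at screening visit, Day 0, Day, 21, Day 49 and Day 77" and omits Days 35 and 63. The protocol does not support this either. Section 3.3 has staff complete the calendar back to the last visit, and section 3.4 describes it as a retrospective method. A missed Day 35 or Day 63 would normally be recovered at Day 49 or Day 77, so no weight should rest on that example.

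The word maximum proves little by itself. Visits may move by 3 days, so the interval between the Day 21 and Day 77 visits can exceed 56 days and a cap has an ordinary purpose. The point rests on the constant divisor, not on that word.

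Dividing by available days has an assumption of its own: that leftover days resemble the subject's valued days. If data are missing not at random, this may be wrong. It is still less extreme than treating all of them as non-heavy.

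Lastly, section 8.2 refers statistical detail to the statistical analysis plan, which is not at hand. The order of imputation and scoring may be settled there. The formula, however, is stated in the protocol, and as stated it is right only for a complete window.

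**Conclusion.** The point holds in a limited form. The HDD 21-77 formula is correct when all 56 days have a measured or imputed value. In the branch that the protocol leaves open, it scores each leftover day as non-heavy. The cost is about 0.075 to 0.175 heavy days per 14 for each such day. A 10-point imbalance between arms would shift the proportion of heavy days by 0.03 to 0.07, or 20% to 47% of the 0.15 detectable difference. These sizes rest on an assumed heavy-day share of 0.3 to 0.7. The protocol gives no reason to expect a 10-point imbalance after imputation, so that figure is illustrative and not a forecast. The sample size is unaffected. The change is worth making because the endpoint is primary and its validity should not depend on a discretionary imputation step.

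**What to change.** In Protocol section 8.2, define HDD 21-77 as

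14 × (heavy drinking days in the window) / (days in the window with a measured or imputed value),

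computed after the calendar imputation in the same section. Use this formula for the modified intention-to-treat and per-protocol analyses and for every sub-period of the 8 weeks, so that no separate divisor is needed for each.

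The cost is a sentence or two in one section and the matching line in the analysis program. No new data are needed, and the score is identical for every subject with 56 valued days. Tabulating valued days by arm alongside the result would show whether the choice mattered.

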- Draw blood for safety parameters, AST, ALT, PC, glucose, creatinine, Na+/K+, Hb, LPK, TPK and hsCRP
- Draw blood for efficacy parameters B-PEth, CDT and GGT
- Perform dip stick tests for U-tox and U-hCG (pregnancy status, females only)
- Collect demographic data
- Complete questionnaires: VAS craving, AUDIT, DUDIT, ASRS, MADRS, Alcohol quantity frequency, nicotine quantity frequency and TEPS
- Administer CPTA test via iPod.
- Control and confirm (except B-Peth criteria) eligibility

Visit 2. Randomization Visit. Accepted range: Maximum 10 days from screening visit

The eligibility criteria based on blood sample analysis are checked and signed by medical doctor. If non-eligible and if required by medical condition the study seeking subject may be referred to appropriate clinic. The eligibility criteria are again confirmed. Medical status and concomitant medication is checked if case status has changed since screening. Data on alcohol consumption since last visit is collected by TLFB. Vital signs and blood samples for outcome specific measurements are collected. Urine sample for pregnancy and toxicology are collected. The subject is randomized to the trial and patient emergency card is handed out.

Saliva sample is collected for cotinine (nicotine metabolite) determination. The IMP is distributed according to randomization list. Patient emergency card is handed out. The study participants will be instructed to start taking the study drug on the following morning, the day after the randomization visit.

Before randomization

- Perform dip stick tests for U-tox, and pregnancy status (if applicable)
- Collect vital signs: Blood pressure, heart rate (after 10 min rest)
- Complete TLFB alcohol calendar since last visit
- Administer VAS craving questionairre
- Check and confirm that medical status is unchanged since screening visit
- Check and confirm eligibility criteria in eCRF system (in order to do this, all above measures must be entered in eCRF)
- Randomization
- Distribute patient emergency card
- Collect concomitant medications if any
- Collect AEs if any
- IMP distribution
- Perfrom saliva dip stick test for cotinine determination
- Collect blood for B-PEth, CDT and GGT analyses

Visit 3. Core battery visit. Accepted range +/- 3 days from scheduled visit date

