7. SAFETY

7.1. Reference Safety Information

This section gives a reference safety information for the conductance of the trial and for the use of VAR in the dose of 1 mg x 2 daily and BUP in the dose of 150 mg x 2 daily, in combination and alone.

A comment regarding reported side effects of VAR and BUP in studies in nicotine dependence is that smoking cessation with or without treatment is associated with nicotine withdrawal symptoms and thus possible exacerbation of underlying psychiatric illness. Not all patients in these reports had known pre-existing psychiatric illness and not all had discontinued smoking. The exact role of VAR and BUP in these reported AEs is not known. Note that depressed mood, which in rare cases may include suicidal ideation or suicidal attempt, can be a symptom of discontinuation of nicotine use.

IMP 1: Varenicline Reference Safety Information

Varenicline in AUD population

VAR in the dose of 1 mg + 1 mg daily for 12 weeks has previously been assessed in subjects with AUD in clinical trials and reported to be safe and well tolerated (see sections 1.1 and 1.2). The adverse events (AEs) were generally of mild character and in concordance with the expected side effects (from the indication nicotine use disorder). With a prevalence of 30%, the most frequent reported AE was **nausea**, followed by

abnormal dreams, constipation, and dysgeusia. The nausea was generally mild or moderate in intensity and seldom resulted in discontinuation. Nausea was most often experienced during the first week of treatment and did not constitute a tolerability concern (Litten et al., 2013;de Bejczy et al., 2015).

Possible action to take to alleviate nausea side effects. If a nausea judged to be possibly related to IMP and judged to be clinical significant by medical doctor, meclozine oral tablets of 25 mg (Postafen®) may be prescribed during the first 14 days of the treatment period to alleviate the initial side effect.

Medical risks associated with varenicline

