Renal and urinary disorders	
Uncommon	Pollakiuria, nocturia
Rare	Glycosuria, polyuria
Reproductive system and breast disorders	
Uncommon	Menorrhagia
Rare	Vaginal discharge, sexual dysfunction
General disorders and administration site conditions	
Common	Chest pain, fatigue
Uncommon	Chest discomfort, influenza like illness, pyrexia, asthenia, malaise
Rare	Feeling cold, cyst
Investigations	
Common	Liver function test abnormal
Rare	Semen analysis abnormal, C-reactive protein increased, blood calcium decreased

* Frequencies are estimated from a post-marketing, observational cohort study

Table 6. Adverse Drug Reactions of Varenicline

Reported adrevers events of varenicline in subjects with AUD

The most prevalent AEs in the varenicline group were nausea (48.1% vs 12.0%), headache (22.1% vs.15.7%) and fatigue (22.1 vs. 10.8%) (de Bejczy et al., 2015). Nausea and abnormal dreams (16.9% vs. 3.6%) were significantly greater in the VAR group compared to placebo (de Bejczy et al., 2015). The AEs that differed significantly between VAR and placebo were nausea (37.1 vs 17.8%), abnormal dreams (27.8% vs. 11.9%) and constipation (9.3% vs 2.0%) (Litten et al., 2013). Compared with placebo, varenicline did not increase suicidal ideation, mood changes or agitation in either study. In sum, the AEs among subjects with AUD are consistent with the side-effects listed in the table above (and ad in SmPC).

Varenicline overdose

No specific antidote for VAR is known. In the event of overdose, hospitalization is advised and management should be as clinically indicated. Hemodialysis may be considered in cases of overdose. No clinically meaningful changes in laboratory test results were observed in the previous clinical trials, nor were there

noteworthy changes in the QT/QTc interval or any other ECG parameter in either preclinical or clinical studies.

Varenicline contraindications

Varenicline is contraindicated in pregnant or nursing women and in patients less than 18 years of age. These are exclusion criteria.

IMP 2: Bupropion Safety Reference Information

Bupropion in AUD population

No controlled clinical trials have assessed BUP in alcohol dependent subjects. However, in the clinical trials assessing combination therapy with VAR and BUP for smoking cessation, alcohol consumption has not been excluded.

Medical risks associated with bupropion

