8. STATISTICS

8.1. Sample size calculation

The power analysis is based on two independent primary hypotheses;

- B-PEth differs significantly between VAR and BUP in combination and alone versus placebo
- Proportion of heavy drinking days (HDD) differ significantly between VAR and BUP in combination and alone versus placebo

Concerning B-PEth, we assume that we can use ordinary t-tests based on normal distribution, with $\alpha=0.025$, $1-\beta=0.80$ and using a standard deviation of 0.8 (previous results from (de Bejczy et al., 2015)). Recruiting 320 patients, randomized in 4 groups of 80 each, we get a detectable effect of 0.35 umol/l and a Cohen's d of 0.44. With regards to HDD, we assume that we can use ordinary t-tests based on normal distribution, with $\alpha=0.025$, $1-\beta=0.80$, using a standard deviation of maximum 0.35 (previous results from (Litten et al., 2013)). Recruiting 360 patients, randomized in 4 groups of 90 each, we get a detectable effect of 15% and a Cohen's d of 0.43. Hence, a sample size of approximately 360 patients should be randomized.

Drop-out rate

Based on prior studies (de Bejczy et al., 2015) with similar design and outcome, the drop-out rate is estimated to approx. 20 % between screening and randomization and approx. 6.5% for randomization to subjects included in modified ITT. To balance the drop-out, 380 subjects are estimated for randomization to reach 360 subjects in the modified ITT.

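### The mITT rule excludes subjects who took study drug but were never reached again, so the HDD comparison can lose early failures unequally by arm

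*Protocol*

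**What the plan says.** Section 8.2 of the protocol defines the mITT set as "all trial subjects who complete screening visit and randomization visit and report that they have taken at least one dose of the randomized IMPs". The only other efficacy set, per protocol, is a subset of it. The text also speaks of an ITT set, but no set of all randomised subjects is defined.

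On the first dose, section 3.3 (Visit 2) says: "The study participants will be instructed to start taking the study drug on the following morning, the day after the randomization visit". The next scheduled contact, and the first pill count, is Visit 3 at Day 7: "Visit 3. Core battery visit. Accepted range +/- 3 days from scheduled visit date".

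Section 8.1 plans for the loss at this step, "approx. 6.5% for randomization to subjects included in modified ITT", and concludes that "380 subjects are estimated for randomization to reach 360 subjects in the modified ITT".

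For missing drinking data, section 8.2 carries the baseline observation forward when a subject drops out early. All other variables, B-PEth included, are left missing.

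**The concern.** Leaving out subjects who never took a capsule is defensible in a blinded trial, because the drug cannot have caused their departure. This rule, however, tests whether a dose was reported, not whether it was taken. If nobody reaches the subject after Day 0, one who took capsules, felt unwell and disappeared cannot be told apart from one who never opened the kit. Both are removed.

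The protocol gives a reason why the first kind of loss might differ by arm. Section 7.1 says of varenicline: "Nausea was most often experienced during the first week of treatment". It reports nausea at 48.1% against 12.0% on placebo in one alcohol trial and 37.1% against 17.8% in the other.

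These are also the early drop-outs for whom section 8.2 provides baseline carried forward. Their baseline HDD exists from the 30-day TLFB calendar at screening, so the rule could be applied without further contact. The set definition removes them first. At stake is a modest tilt of the HDD comparison towards arms with more early loss, which no defined efficacy set would reveal.

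**Working it through.** **1. The plan's own figures.** To end with 360 at 6.5% loss: 360 / (1 − 0.065) = 385.03, rounded up to 386, against 380 stated. Forwards, 380 × 0.935 = 355, against 360 stated. Both agree within 3%. The budgeted loss is therefore 380 − 360 = 20 to 0.065 × 380 = 24.7, or about 5 to 6 per arm of 95.

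Yardstick for HDD (section 8.1: SD 0.35, 90 per arm, power 0.80, alpha 0.025 read as one-sided): 0.35 × √(2/90) × (1.960 + 0.842) = 0.146, against 15 points stated.

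**2. Formula.** Let p_a and p_p be the proportions excluded on active and placebo, and r_a and r_p the fall in the HDD proportion among those retained. Excluded subjects get zero change, as baseline carried forward implies.

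- mITT contrast: r_a − r_p
- Contrast with the excluded kept: r_a(1 − p_a) − r_p(1 − p_p)
- Gap: r_a·p_a − r_p·p_p, which is (p_a − p_p) × r if both arms fall by the same r

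**3. Numbers.** The protocol gives no loss by arm and no HDD fall, so p and r are assumptions. All excluded subjects are treated as dosed but unreached.

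| Loss, active vs placebo | r | Gap in points | Share of 15 points |
|---|---|---|---|
| 7.5% vs 3.5% | 0.2 | 0.04 × 0.2 = 0.8 | 5% |
| 7.5% vs 3.5% | 0.3 | 0.04 × 0.3 = 1.2 | 8% |
| 9% vs 4% | 0.2 | 0.05 × 0.2 = 1.0 | 7% |
| 10% vs 3% | 0.3 | 0.07 × 0.3 = 2.1 | 14% |

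**4. Fit to the budget.** Three of the four arms are active. (3 × 7.5% + 3.5%) / 4 = 6.5%, so the first pair of rows matches. With all three active arms at 9–10%, the average is (3 × 9% + 4%) / 4 = 7.75% to (3 × 10% + 3%) / 4 = 8.25%, above budget. The last two rows match 6.5% only if bupropion alone behaves like placebo: (2 × 9% + 2 × 4%) / 4 = 6.5% and (2 × 10% + 2 × 3%) / 4 = 6.5%.

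**5. Unequal falls.** If retained subjects on drug improve more, the gap widens. With r_a = 0.30, r_p = 0.15 and losses of 10% vs 3%: 0.10 × 0.30 − 0.03 × 0.15 = 0.0255, so an mITT contrast of 15 points becomes about 12.5. Not all of this comes from unequal loss: equal loss of 6.5% alone gives 0.065 × 0.15 = 1.0 point.

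**6. B-PEth.** The primary variable is the mean over Day 21 to Day 77. A subject lost in week 1 has no such sample and nothing is imputed, so a wider mITT set would not bring that subject into the analysis.

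**The case against.** A reader might infer that anyone who stops in week 1 and does not come back to the site is dropped. The protocol does not support that. The rule asks for a report and names no visit or place. Sections 3.3 and 4.4 give discontinued subjects an end-of-treatment visit and an adverse-event call at day +7, section 7.3.1 requires an assessment after stopping for an adverse event, and an available phone number is an inclusion criterion. One report of a dose through any of these admits the subject, and the early drop-out rule then applies. The affected group is only those never reached at all. It can still exist: section 4.4 lists loss to follow-up as a reason for discontinuation.

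The evidence for unequal loss is indirect. The nausea rates are adverse-event incidences for varenicline, not week-1 losses. Section 7.1 twice says that nausea seldom led to discontinuation, and that it was not a tolerability concern. That stands and limits the likely size. The 6.5% also covers subjects who never took a dose and, under section 8.2, those randomised in error, which leaves less room for a gap between arms.

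A reader might extend the point to the safety set, which uses similar wording. That does not work: the safety set separately requires post-dose data, which an unreached subject lacks whatever is presumed about dosing.

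Lastly, how a dose is evidenced might be left to the statistical analysis plan, which was not available here. But the protocol itself fixes the entry condition as the subject's report, and that condition settles the unknown cases as exclusions.

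**Conclusion.** The point holds in a limited form. The mITT definition makes a post-randomisation exclusion that treatment can influence, confined to subjects who took study drug and were never reached after Day 0. It affects the HDD primary endpoint and leaves B-PEth essentially unchanged.

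Its size cannot be fixed from the protocol. Under assumptions that match the 6.5% budget with all active arms alike, the bias towards drug is about 0.8 to 1.2 percentage points. It reaches about 1 to 2 points if early loss is concentrated in the two varenicline arms. All these figures rest on assumed losses by arm, an assumed equal HDD fall of 0.2 to 0.3 among those retained, zero change in the excluded, and every loss being a dosed but unreached subject. This is a modest distortion against a 15-point detectable effect, but it is avoidable.

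**What to change.** Define mITT as all subjects randomised and dispensed study drug, excluding only those for whom a returned kit or a contact documents that no capsule was taken. Subjects with no information stay in, and their HDD follows the existing early drop-out rule in section 8.2. Report the number excluded from mITT, by arm and reason. Leave the safety set as it is on this point.

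The cost is a change of wording; no new data are needed. The downside is that a few subjects who never took a dose may be kept, which slightly dilutes the estimated effect.
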